5.3.3 Severity of COPD

Severity of COPD will be evaluated among new users of olodaterol and indacaterol that are aged 40 years or older and have a recorded diagnosis of COPD (with or without a diagnosis of asthma) ever before or up 30 days after the index date. The population aged 40 years or older is considered the most likely to have COPD and is frequently selected in studies to evaluate medication use among patients with COPD [[P07-07347](#), [P11-13226](#), [P07-09136](#)]. Patients aged 39 years or younger with a diagnosis of COPD will still be considered as

Proprietary confidential information © 2017 Boehringer Ingelheim International GmbH or one or more of its affiliated companies

having COPD and described separately if there are at least 5 patients in each COPD severity category. Definitions shown in [Table 8](#) will be adapted to the characteristics and data availability in each data source; database-specific specifications have been described in [Section 9.2](#). The four severity categories will be mutually exclusive, and patients that fulfil criteria for more than one category will be classified as being in the more severe category.

Table 8 Definition criteria of COPD severity (adapted primarily from Verhamme et al., 2012 [[P11-13226](#)])

Severity of COPD	Definition
Mild	Less than two prescriptions/dispensings of drugs for obstructive airways disease of the same class in any 6-month interval in the 12 months before the index date (i.e., 0 or 1 prescriptions/dispensings of the same COPD drug class in the 12 months before the index date, or if ≥ 2 prescriptions/dispensings, these have to be more than 6 months apart)
Moderate	Regular bronchodilator treatment, defined as having at least two prescriptions/dispensings of the same COPD drug class with an interval of ≤ 6 months in the 12 months before the index date ^{1,2}
Severe	Occurrence of at least one of the following events in the 12 months before the index date: 
 • Hospitalisation for COPD exacerbation¹ • At least two COPD exacerbations without hospitalisation, where COPD exacerbation is defined by any of the following³: 
 • A course of antibiotics for lower respiratory tract infection (acute bronchitis or pneumonia)¹ • A course of systemic corticosteroids for the treatment of COPD exacerbation¹ • A diagnoses of COPD exacerbation without hospitalisation
Very severe	Occurrence of at least one of the following events in the 12 months before the index date unless another time period is specified: 
 • Dispensed oxygen therapy^{1,2} • Dispensed nebuliser therapy^{1,2} • Diagnosis of emphysema at any time before the index date¹

COPD = Chronic Obstructive Pulmonary Disease.

- 1 Severity criteria also included in definition from Curkendall et al., 2006 [[P07-09136](#)].
- 2 Severity criteria also included in definition from Soriano et al., 2001 [[R08-1492](#)].
- 3 Severity criteria modified to align with the Global Initiative for Chronic Obstructive Lung Disease (GOLD) 2016 definition for severity categories C and D [[P16-00121](#)]. If two or more of these criteria occur within a 21-day time period, they will be considered part of the same exacerbation episode and counted only once. If one or more of these criteria occur within a 21-day period of a hospitalisation for COPD, this will be considered part of the same “COPD exacerbation with hospitalisation” episode.

Sources: modified from Verhamme et al., 2012 [[P11-13226](#)]; Soriano et al., 2001 [[R08-1492](#)]; Curkendall et al., 2006 [[P07-09136](#)]; and GOLD, 2016 [[P16-00121](#)].

Because data on hospitalisations are not available in the IMS RWE LPD database, COPD severity will not be described in this database.

The proposed operational definitions to be applied when assessing the severity of COPD are as follows:

- Same-class “drugs for obstructive airways disease”: medications listed in [Annex Table 1-6](#) will be identified through prescriptions/dispensings for the list of medications of interest recorded in the database within 12 months before or on the index date and classified into one of the following drug classes:
 - Bronchodilators: inhaled short-acting muscarinic antagonists (SAMAs), inhaled LAMAs, inhaled short-acting beta2-agonists (SABAs), inhaled LABAs, and fixed combinations of SABAs and SAMAs
 - Inhaled glucocorticosteroids: ICS alone, fixed combinations of SABAs and ICSs, and fixed combinations of LABAs and ICSs
 - Systemic glucocorticosteroids
 - Systemic beta2-agonists
 - Xanthines
 - Roflumilast
- Hospitalisation for COPD exacerbation: an inpatient (primary or secondary discharge) code for COPD (ICD-10 codes: J41-J44), acute bronchitis (ICD-10 codes: J20, J21, J22, J40), or pneumonia (ICD-10 codes J09, J18) within 12 months before or on the index date.
- At least two COPD exacerbations without hospitalisation, where COPD exacerbation is defined by any of the following: a course of antibiotics, a course of systemic glucocorticosteroids, or a diagnosis of COPD exacerbation (including COPD exacerbation diagnosis *per se*, acute bronchitis, or pneumonia) during the 12 months before or on the index date. To identify exacerbation episodes, a 21-day time period will be used [[R16-1576](#)]; consecutive prescriptions of antibiotics, systemic glucocorticosteroids, or diagnosis codes for COPD exacerbation within 21 days of the first record of each episode will be considered to be a single exacerbation. When there is a hospitalisation within 21 days of the COPD exacerbation, this will be counted as one “hospitalisation for COPD or COPD exacerbation with hospitalisation.” The number of exacerbations without hospitalisation will be further categorised into 0 to 1 or ≥ 2 .
- A course of antibiotics: all dispensings for country-specific antibiotics used to treat lower respiratory tract infections (acute bronchitis or pneumonia) during the 12 months before or on the index date will be identified (a list of Anatomical Therapeutic Chemical [ATC] codes will be developed in each data source and will include those that are specific to treat the disease in each country). A course of antibiotics will be defined as treatment involving consecutive dispensings of antibiotics with less than 7 days between the end of days of supply of one dispensing and the date of the next dispensing. The variable “second course of antibiotics” will be categorised as “no” if the patient had 0 or 1 course of antibiotics during the 12 months before or on the index date, or “yes” if the patient had at least two courses of antibiotics during the 12 months before or on the index date.
- A course of systemic glucocorticosteroids: all dispensings for country-specific systemic glucocorticosteroids used to treat COPD, such as prednisolone and prednisone, during the 12 months before or on the index date will be identified (a list of ATC codes will be developed in each data source and will include those that are specific to treat the disease

in each country). A course of systemic glucocorticosteroids will be defined as treatment involving consecutive dispensings of systemic glucocorticosteroids with less than 7 days between the end of days of supply of one dispensing and the date of the next dispensing. The variable “second course of systemic glucocorticosteroids” will be categorised as “no” if the patient had 0 or 1 course of systemic glucocorticosteroids during the 12 months before or on the index date or “yes” if the patient had at least two courses of systemic glucocorticosteroids during the 12 months before or on the index date.

- Diagnosis of COPD exacerbation without hospitalisation: an outpatient (GP, outpatient hospital clinic, or pulmonologist) ICD-10 code or ICPC code for COPD exacerbation (ICD-10 code: J44.1; free-text search in the PHARMO-GP), acute bronchitis (ICD-10 codes: J20, J21, J22, J40; ICPC code: R78), or pneumonia (ICD-10 codes: J09-J18; ICPC code: R81) within 12 months before or on the index date.
- Oxygen therapy: a prescription or dispensing for oxygen therapy (ATC code: V03AN01) within 12 months before or on the index date.
- Nebuliser therapy (to be identified in each data source using national drug codes).
- Emphysema: an outpatient or inpatient (primary or secondary hospital discharge or outpatient hospital clinics) code for emphysema at any time before or on the index date (ICD-10: J43; free-text search in the PHARMO-GP).

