5. OUTCOMES

For each patient, the observation period will start at the index date and look retrospectively for all available historical data and prospectively for up to 30 days after the index date to identify potential off-label use (Figure 1). The index date is defined as the date of the first recorded dispensing/prescription of olodaterol or indacaterol during the study period in each data source (see Table 1). In each country, new users of olodaterol and indacaterol will be identified in the databases, which record information on the medications prescribed by the physicians or dispensed by pharmacies. Evaluation of off-label use and diagnosis of COPD, asthma, or other respiratory conditions will be assessed using all available information in the database before the index date (as far back in time as records in the data source are available)—i.e., 01 Jan 1994 in Denmark, 1998 in PHARMO (1998 for total patient set and 2006 for subset with GP data available), and 1994 in IMS RWE LPD (1994 for GP panel and 2007 for pulmonologist panel) and up to 30 days after index date. Characterisation of new users based on demographic and other non-respiratory comorbidities will be assessed using all available information in the database before the index date, unless otherwise specified. Medication use, severity of COPD, and health care resource utilisation will be assessed for the 1-year period before the index date. Database-specific specifications to define the variables of interest in each data source are included in Section 9.2.

Figure 1 Time periods for defining key study variables

^a“Other respiratory conditions” are respiratory comorbidities other than COPD or asthma recorded at any time before or up to 30 days after index date and will be ascertained using the diseases and codes listed in Table 8. These will be described for the purpose of characterising the study population overall and the patients classified as potential off-label users.

Proprietary confidential information © 2017 Boehringer Ingelheim International GmbH or one or more of its affiliated companies

The type of data available varies in each database and is summarised in [Table 2](#).

Table 2 Selected characteristics of the study databases

Type of data	PHARMO, the Netherlands	National Registers, Denmark	IMS RWE LPD, France
Hospital inpatient discharge diagnoses	Yes	Yes	No
Hospital inpatient procedures	Yes	Yes	No
Hospital/clinic outpatient diagnoses	No	Yes	No

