5.3.2 Health care resource utilisation

Health care resource utilisation will be evaluated within 12 months before cohort entry but not including the index date. The variables listed in [Table 7](#) will be used to capture the utilisation of health care resources. Additional details on the definition of the variables in each data source are described in Section [9.2](#).

Table 7 Health care resource utilisation variables

Health care resource parameter	Definition and categories	Medications included
All dispensings	Number of dispensings for all medications; ordinal variable with 0, 1-9, 10-19, 20 or more	All medications included in Annex Table 1-6
Dispensings for respiratory medications ¹	Number of dispensings for respiratory medications; ordinal variable with 0, 1-4, 5-9, 10 or more	All medications included in the section on respiratory medications in Annex Table 1-6
Dispensings for systemic glucocorticosteroids	Number of dispensings for systemic glucocorticosteroids; ordinal variable with 0, 1-4, 5-9, 10 or more	ATC code H02AB
Dispensings for LABAs	Number of dispensings for LABAs; ordinal variable with 0, 1-4, 5-9, 10 or more	ATC codes R03AC012 (salmeterol) and R03AC013 (formoterol)
Hospitalisations	Number of hospitalisations for any cause; ordinal variable with 0, 1, 2, 3-4, 5 or more	To be determined by each data source
Hospitalisations for COPD	Number of hospitalisations with a primary discharge diagnosis of COPD; ordinal variable with 0, 1, 2, 3-4, 5 or more	ICD-10 codes for COPD: J41-J44, or as defined in Section 5.1 for each data source, but limited to inpatient codes
Hospitalisations for asthma	Number of hospitalisations with a primary discharge diagnosis of asthma; ordinal variable with 0, 1, 2, 3-4, 5 or more	ICD-10 codes for asthma: J45, J46, or as defined in Section 5.1 for each data source, but limited to inpatient codes

ATC = Anatomical Therapeutic Chemical; COPD = Chronic Obstructive Pulmonary Disease; ICD-10 = *International Statistical Classification of Diseases and Related Health Problems, 10th Revision*; LABA = Long-Acting Beta2-Agonist.

¹ Study medications will be counted (e.g., when describing the olodaterol cohort, the dispensings of indacaterol will be counted and vice versa).

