5.3.6 Comedications

Characterisation of the patient population will include a description of the prescriptions or dispensings for comedications of interest listed in [Annex Table 1-6](#) that are recorded within 12 months before or on the index date.

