7.2 CONCOMITANT DISEASES AND MEDICATION

Frequency of history of specific diseases and conditions of interest at any time before the index date will be assessed for each exposure group in each data source within the overall study population (Shell Table 5.1 and Shell Table 6.1). The same analysis will be repeated for adults (Shell Table 5.2 and Shell Table 6.2) and for those patients aged 40 years or older with a diagnosis of COPD (Shell Table 5.3 and Shell Table 6.3). Diagnosis of COPD, asthma, and other respiratory comorbidities and time since first COPD diagnosis will be included as part of the description of medical history. In this table, COPD, asthma, and respiratory comorbidities will not be mutually exclusive, and a patient will be allowed to be in more than one group. The comorbidities to be considered are listed in Sections [5.3.4](#) and [5.3.5](#), and a complete list of codes is included in [Annex Table 1-5](#).

The number and percentage of patients with a prescription or dispensing for a specific medication within the year before the index date will be described in each exposure group for the overall population (Shell Table 7.1 and Shell Table 8.1), for all adults (Shell Table 7.2 and Shell Table 8.2), and for those patients aged 40 years or older with a diagnosis of COPD (Shell Table 7.3 and Shell Table 8.3). A description of the medications considered is detailed in Section [5.3.6](#), and the list of codes is presented in [Annex Table 1-6](#).

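### SAP 5.3.3 and 5.3.6 count the index day as prior medication; with Annex Table 1-6 as printed, this adds the index dispensing for indacaterol users but not for olodaterol users

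*SAP*

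**What the plan says.** The SAP gives two different windows for the same variables.

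Windows that stop before the index date:
- SAP Section 5: "Medication use, severity of COPD, and health care resource utilisation will be assessed for the 1-year period before the index date".
- SAP Table 8, Moderate: "at least two prescriptions/dispensings of the same COPD drug class with an interval of ≤ 6 months in the 12 months before the index date". The Mild row uses the same window.
- SAP 7.2, comedications: "a prescription or dispensing for a specific medication within the year before the index date".
- SAP 5.3.2: "Health care resource utilisation will be evaluated within 12 months before cohort entry but not including the index date".
- Protocol 9.3.3 and 9.3.3.6 also take medication use from the 12 months preceding the index date.

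Windows that include the index day:
- SAP 5.3.3, operational definition of same-class drugs: "recorded in the database within 12 months before or on the index date and classified into one of the following drug classes".
- SAP 5.3.6, comedications: "that are recorded within 12 months before or on the index date".

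Both of the latter rules take their drugs from one list. In 5.3.3 the wording is "medications listed in [Annex Table 1-6](#) will be identified through prescriptions/dispensings for the list of medications of interest", and 5.3.6 points to the same table. That table has indacaterol (R03AC18) in the inhaled SABA group. Its inhaled LABA group holds only salmeterol and formoterol. Olodaterol, coded R03AC19 in SAP Table 10, is not in the table.

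For severity, SAP 5.3.3 forms one pooled class: "Bronchodilators: inhaled short-acting muscarinic antagonists (SAMAs), inhaled LAMAs, inhaled short-acting beta2-agonists (SABAs), inhaled LABAs, and fixed combinations of SABAs and SAMAs".

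**The concern.** SAP Section 5 defines the index date as the day of the first study-drug record, and SAP 6.3 requires none before it. Use of a patient's own study drug strictly before the index date is therefore 0% by design. Adding the index day makes it 100% for any study drug on the list. No sentence in the public text removes that record.

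At stake is the baseline description, which is a primary objective for olodaterol and a secondary one for indacaterol. The Mild/Moderate split is meant to describe disease before treatment. Under the literal rule, entry into the indacaterol cohort itself supplies one of the two dispensings needed for Moderate. With the list as printed, two patients with the same history can fall in different severity categories only because one started indacaterol and the other olodaterol. SAP Section 7 has each research centre run its own analysis from this core text, so centres could also choose different windows.

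**Working it through.** The documents state no figure that depends on this window, so there is nothing to reproduce. The check has three parts.

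**1. The rule applied to single histories.** Inputs: the pooled bronchodilator class and the Table 8 thresholds, with 6 months taken as 182 days and no other class or Severe/Very severe criterion met. Day 0 is the index date.

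| Earlier inhaled bronchodilator dispensings | Index day excluded | Index day included, indacaterol (listed) | Index day included, olodaterol (not listed) |
|---|---|---|---|
| None | Mild | Mild | Mild |
| Day −30, −90 or −180 (one only) | Mild | Moderate | Mild |
| Day −200 (one only) | Mild | Mild | Mild |
| Days −300 and −30 | Mild | Moderate | Mild |
| Days −90 and −30 | Moderate | Moderate | Moderate |

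The index dispensing changes the category only if an earlier bronchodilator lies within 6 months of the index date and no two earlier ones are within 6 months of each other. Indacaterol's place in the SABA group does not keep it out of the count, because SABAs and LABAs share one class. A patient with COPD who switched to indacaterol from single-agent salmeterol or formoterol (a different LABA within 3 months, protocol 9.2.3) always becomes at least Moderate.

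**2. Comedications.** Under 5.3.6 all indacaterol users show R03AC18. Because the table files it under inhaled SABAs, a group row built from the table would read 100% SABA use in that cohort. Olodaterol users gain nothing from their own index record.

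**3. Illustrative size.** Assume that earlier bronchodilator dispensings follow a Poisson distribution with mean r per year, spread evenly over 12 months, and that no other class or Severe/Very severe criterion applies. The rates are assumptions; no document gives them.

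- Index day excluded: zero or one dispensing is Mild; two are Mild with probability 1/4 (more than half a year apart); three or more cannot be Mild. P(Mild) = e^(−r)(1 + r + r²/8).
- Index dispensing counted: zero is Mild; one is Mild with probability 1/2 (in the earlier half-year); two or more cannot be Mild. P(Mild) = e^(−r)(1 + r/2).
- Shift = e^(−r)(r/2 + r²/8).

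| r per year | Mild, index excluded | Mild, index counted | Shift (points) |
|---|---|---|---|
| 0.5 | 92.9% | 75.8% | 17 |
| 1 | 78.2% | 55.2% | 23 |
| 2 | 47.4% | 27.1% | 20 |
| 3 | 25.5% | 12.4% | 13 |
| 4 | 12.8% | 5.5% | 7 |
| 8 | 0.6% | 0.2% | 0.4 |

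For r = 1: 0.3679 × 2.125 = 0.782 and 0.3679 × 1.5 = 0.552, a difference of 0.230. Simulation agrees to within 0.4 of a point at each rate. The shift peaks where r² + 2r − 4 = 0, at r = 1.24, with 23.5 points.

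If patients differ in rate (gamma-distributed with mean 1), the shift at 1 per year falls. With shape 1 it is (1/4)/2 + (1/4)/8 = 0.156. With shape 0.5 it is 0.192/2 + 0.192/8 = 0.120.

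**The case against.** Table 8 holds the category rules, and its Mild and Moderate rows end before the index date. The bullets beneath it are called proposed definitions, and the same-class bullet mainly identifies and groups drugs. A programmer who applies the Table 8 window would not count the index dispensing. Footnote 1 of SAP Table 7 illustrates counting only the other study drug in each cohort. The database-specific specifications (SAP Section 9.2) and the table shells are not in the public text and may settle the matter. A row showing 100% indacaterol among indacaterol users would mislead nobody.

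Much of this is fair. The documents do not establish that patients will be reclassified. They establish that two stated windows give different answers and that nothing visible chooses between them. The Table 7 footnote concerns resource use, where the index day is already excluded, so it does not govern 5.3.3 or 5.3.6. The indacaterol row is harmless alone, but a SABA row inflated in one cohort only is not.

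A reader might infer that the index dispensing of olodaterol also moves its users to Moderate. As printed it does not, because R03AC19 is absent from Annex Table 1-6. A reader might also infer that indacaterol is spoiled as a benchmark. In protocol Section 8, the aim of putting the olodaterol results in perspective belongs to the off-label frequency objective. Describing indacaterol users is a separate objective without that aim.

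**Conclusion.** The conflict between windows is real. Followed literally, the operational rules give a wrong result for indacaterol users and leave olodaterol users unchanged. If olodaterol is added to the annex and the window stays as it is, the same self-counting reaches the drug of the primary objective.

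The scope is limited. Off-label classification rests on age and recorded diagnoses (SAP 5.1 and 7.5.1), so its prevalence is unaffected. Severity is not described in the French database; the comedication rule applies in all three sources.

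The size cannot be known from the documents. The illustration runs from 0.4 to about 23 points depending on the assumed rate. Quoting only 13 to 23 points would reflect a choice of rates between 0.5 and 3 per year. The shift over all patients with COPD would be smaller than the illustration, because some are already Moderate through another drug class and others are Severe or Very severe. The conclusion also assumes that the unseen Section 9.2 and table shells do not already exclude the index record.

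**What to change.** 1. In SAP 5.3.3 and 5.3.6, state that the study-drug record on the index date (R03AC18 or R03AC19) is not counted.
2. In 5.3.3, set the same-class window to the 12 months before, and not including, the index date, as in Table 8 and in line with 5.3.2.
3. Reconcile the other 5.3.3 bullets that include the index day (hospitalisation, exacerbations, antibiotics, systemic glucocorticosteroids, oxygen, emphysema) with Table 8.
4. List both study drugs under inhaled LABAs in Annex Table 1-6. Do this together with step 1, so that self-counting does not spread to olodaterol. It also lets the cross-cohort counting in footnote 1 of SAP Table 7 work in both directions.
5. If other drugs dispensed on the index date are of interest, report them separately as co-dispensed at index.

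The cost is a few phrases in the SAP, two annex entries and one program filter per centre. No new data are needed.
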